#### Improving Driving in Adults with Autism Spectrum Disorders PI: [name]

lowest left rib. This placement has been found minimize movement artifact induced by fundamental vehicle control (i.e. steering) while also involving minimal intrusiveness during placement. Skin conductance is measured using a constant current configuration and non-polarizing, low-impedance gold-plated electrodes. The skin conductance electrodes will be placed on the underside of outer segments of the ring and middle finger of the left hand. Data sampling is carried out at a rate of 250 Hz to provide sufficient resolution for detecting the ECG R-wave to calculate heart rate. Where appropriate, statistical computations for physiological data will be completed based upon transforms designed to control for individual variability. Eye glance behavior will be coded from the in-cab video recordings and reduced to numeric values prior to further analysis. Source data will be labeled with subject identification numbers and maintained on password access controlled computers.

At each of the driving simulation visits, subjects will complete some questionnaires. The preexperiment questionnaire includes the Beck Anxiety Inventory (BAI), which is a 21-item selfreport inventory that is used for measuring the severity of anxiety in children and adults. Each question on the BAI is scored on a scale value of 0 (not at all) to 3 (severely), and higher total scores indicate more severe anxiety symptoms. Also included in the pre-experiment questionnaire is a standard MIT short questionnaire that includes basic demographics, driving history information, a state anxiety checklist, and a sleep-awake scale.

For the actual driving simulation, subjects will be seated in the driving simulator and introduced to interacting with the simulation environment through a brief adaptation drive of approximately 10 minutes. This training drive will begin under low speed and with no oncoming traffic. The speed limit will be gradually increased along with increased visual complexity of the roadway and density of on-coming traffic. This gradual increase in visual complexity follows guidelines designed to reduce the likelihood of simulator sickness. This period is also intended to allow subjects the opportunity to become accustomed to the mechanisms of the simulator and to reduce the novelty of driving the simulator.

Following the adaptation period, subjects will be asked to "stop" the vehicle. A staff member will check with the subject to see if they are comfortable to proceed with the study. Upon accent to continue, the general characteristics of the primary drive will be explained and any questions that the subject has will be answered. The driving protocol will include periods of both high and low task stimulation. If the subject follows typical travel behavior based upon posted speed limits and surrounding traffic flow, the duration of the primary drive should run for approximately 45 minutes. As described previously, the primary dependent measures collected during the simulated drive will focus on driving performance related eye glance / scanning behavior and physiological measures indicative of relative arousal levels (heart rate and skin conductance). Other driving performance metrics related to variables such as speed control and lane discipline maintenance will be collected as secondary measures.

After the simulation, subjects will complete the post-experiment questionnaire, which includes the short state anxiety scale and questions about the subject's experience in the simulator. Subjects will also complete the Kennedy Simulator Sickness Questionnaire, which is a 16-item questionnaire to assess the extent to which simulator sickness may have been experienced. Each experience is rated on a scale of 1 (None) to 4 (Severe).

Subjects will be compensated by MIT \$60 at the completion of each of the two driving simulation visits (\$120 total) for the MIT portion of the study.

During study participation, if an individual expresses spontaneous suicidality or endorses suicidality through any study questionnaires or procedures, the principal investigator of the study will be contacted immediately via phone or page to assess the risk of the current situation and recommend a suggested plan of action to assist the current participant. The participant may be referred to the emergency department for immediate evaluation upon recommendation of the principal investigator.

The Institutional Review Board at Massachusetts Institute of Technology will review the driving simulation protocol. No study procedures will be performed until IRB approval is granted from both institutions, and the MIT IRB approval letter is submitted the PHRC for approval.

# V. BIOSTATISTICAL ANALYSIS

Our tests of hypotheses will rely heavily on random regression models (RRM) [also known as the hierarchical linear model and random (or mixed) effects model]. This approach has several advantages over traditional methods such as repeated measures ANOVA or MANOVA. We will estimate our RRMs using the generalized estimating equation (GEE) framework. Canonical links will be used to correctly model the distribution of dependent variables. For binary outcomes, logistic regression models will be fit with the binomial family and the logit link. For count data, Poisson regression models will be fit with the Poisson family and the log link, and for normally distributed data, linear regression models will be fit with the Gaussian distribution and identity link. Working covariance structures will be specified with Huber-White robust estimators of variance to account for repeated measures of each subject.

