One such intervention is the atypical anxiolytic medicine busporine. Unlike other anxiolytics, the pharmacology of buspirone is not related to that of benzodiazepines, barbituates or carbamates (it is not a GABA receptor agonist) and so buspirone does not carry abuse potential risk for which other anxiolytics are known. As such, buspirone is not considered to be a drug-of-abuse and is unscheduled. Buspirone is rapidly acting and non-sedating. It is also a very safe medicine with a benign adverse effect profile, no meaningful drug-drug interactions, and lacks withdrawal reactions. Because of its short duration of action, it can be used on as needed basis making it an ideal and safe compound to target driving-induced anxiety in HF-ASD individuals. The main aim of the current study is to test the hypothesis that pharmacological pre-treatment (2 days before and during the simulation) of adult drivers with HF-ASD with low doses of buspirone (5.0 mg BID) will be associated with reduction in hyperarousal as measured by elevated heart rates and abnormal skin conductance, and improvement in driving performance in a simulator as measured by eye tracking deviations. To this end, we propose to conduct a randomized cross-over trial of treatment with buspirone for 2 days before and during the simulation in 24 HF-ASD subjects using an AB-BA design.

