## III. SUBJECT ENROLLMENT

We propose to enroll 24 adult drivers with HF-ASD. Subjects will be males and females, ages 18-45, with a diagnosis of DSM-V Autism Spectrum Disorder. Potential subjects will be recruited from advertising in the local media (newspapers, radio, etc.), MBTA advertisements, flyers posted in the local community and on college campuses, and through the MGH recruitment website, Rally. Potential subjects may also be recruited from local associations that provide programming for individuals with HF-Autism Spectrum Disorder (e.g. AANE, Aspire) or through outpatient clinics at MGH that service individuals with HF-ASD. If a potential subject expresses interest to participate in the study via email, the coordinator will reply and instruct the subject to review the Partner's required language surrounding encrypted and unencrypted emails and will verify their preference prior to proceeding with email communication.

A brief phone screen will be completed with subjects who are interested in participating in the study by a member of study staff. The phone screen asks some questions regarding medical and psychiatric history. If the subject is eligible after the screen, a member of study staff will schedule a time for them to come into the office.

Informed consent will be obtained by a licensed physician investigator prior to the performance of any study procedures. The informed consent will be used to explain, in simple terms, the risks and benefits of study participation to the subject. The subjects may take as much time as they feel necessary to consider their participation in the study, as well as consult with their family members or a physician.

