### IV. STUDY PROCEDURES

Completion of this study will be dependent on the availability of the participant and includes a clinical assessment visit at Massachusetts General Hospital and two driving simulation visits (approximately 1.5 hours each) at Massachusetts Institute of Technology.

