## **Driving Simulation Visits**

Previous work between MGH and MIT utilized the simulator that will be used in this study . After completion of the Assessment Visit, the subject will schedule the two driving simulation visits at Massachusetts Institute of Technology during this time they will be given or emailed an information sheet regarding what the MIT driving simulation visit will entail. Each driving simulation visit will be approximately 1.5 hours long. At the first driving simulation visit, subjects will be asked to review and sign the MIT consent form before proceeding.

Half of eligible and consenting subjects (A-B group) will be tested on the driving first on medication while the other half (B-A group) will be tested first unmedicated based on a randomization list. The subjects will be instructed to take 5.0 mg of buspirone with breakfast and 5.0mg of buspirone with dinner for 2 days before their driving simulation. On the day of the simulation, they will be instructed to take the dose 1 hour before the simulation. A member of study staff will remind the subjects via phone call and/or email to take their medication on the two days preceding their driving simulation, and remind them of the specific times at which they should take the medication.

If a subject is assigned to the A-B group per the randomization list, they will receive the buspirone at the completion of their assessment visit at MGH. A member of study staff will remind the subject that they should not take the medication until 2 days before the driving simulation. Written instructions will also be provided explaining the dates and times when the medication should be taken. If the individual is currently taking buspirone they will be instructed to take the busiprone, as prescribed, prior to their first simulation visit. However, prior to their second simulation visit with MIT they will be asked to withhold their medication starting 24 hours prior to their second visit.

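### Section V names a mixed model but estimates it by GEE with no working correlation; with 24 subjects, an uncorrected robust test rejects about 7–8% of true nulls at nominal 5%

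*Combined protocol and SAP*

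**What the plan says.** Section V (Biostatistical Analysis) rests the hypothesis tests on random regression models, which it glosses as "also known as the hierarchical linear model and random (or mixed) effects model". It then gives the estimation method: "We will estimate our RRMs using the generalized estimating equation (GEE) framework". Links follow by outcome type: logit for binary, log for counts, identity for Gaussian data. Repeated measures are covered by one sentence: "Working covariance structures will be specified with Huber-White robust estimators of variance to account for repeated measures of each subject".

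The section gives no working correlation, random effect, model terms (such as period), significance level, small-sample correction, or rule for a subject with only one drive. No other section supplies them.

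The design is a randomised crossover "in 24 HF-ASD subjects using an AB-BA design" (Section I), with half the subjects driving first on medication and half first unmedicated (Driving Simulation Visits). Each subject has "two driving simulation visits (approximately 1.5 hours each) at Massachusetts Institute of Technology" (Section IV). Section VI acknowledges simulator sickness and lets subjects stop whenever they wish.

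**The concern.** A mixed model describes within-subject dependence through a subject effect and is usually fitted by likelihood or REML. GEE models only the marginal mean; it treats the dependence as a working assumption and repairs the standard error with a sandwich estimator. Two analysts could follow Section V in good faith, fit different models and report different p-values. If the choice is left open, it may be made after the data are seen.

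Three things are at stake.

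- **Type I error.** The sandwich variance is a large-sample device. With 24 clusters and no correction it is too small on average.
- **Precision.** A crossover gains by weighting the two drives of a subject as a pair. The working correlation supplies that weighting in GEE, and it is unnamed. This matters only when pairs are incomplete.
- **Missing second drives.** Unweighted GEE generally needs them to be missing completely at random, whereas a likelihood-based mixed model needs only missing at random. A subject who has a bad first drive may not come back.

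**Working it through.** The plan gives no power, alpha, effect size, SD, within-subject correlation or drop-out rate, so it has no figure to reproduce.

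**Inputs from the document:** 24 subjects (Section III), AB-BA (Section I), half per sequence, so 12 + 12 (Driving Simulation Visits), two drives each (Section IV), Gaussian outcome with identity link, Huber-White variance (Section V).

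**Assumptions:** total SD 1; within-subject correlation ρ of 0.5 to 0.8; about 15% of second drives missing; treatment and period in the model; two-sided 5%; robust statistic compared with 1.96.

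**1. Type I error, complete pairs.** Let d be each subject's on-minus-off difference and SSW the sum of squares of d about its sequence mean. The treatment estimate is the average of the two sequence means of d.

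- Usual variance: SSW/(22 × 24), with a t reference on 22 degrees of freedom.
- Uncorrected sandwich variance: SSW/24² = SSW/576.
- Ratio, sandwich to usual: (22 × 24)/576 = 0.917.

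The robust z is therefore √(24/22) times the t statistic. Rejecting when |z| > 1.96 means rejecting when |t| > 1.96 × √(22/24) = 1.877. On 22 degrees of freedom with normal data, that has probability 0.074. The test is thus 7.4% in place of 5%, whatever ρ is. Simulation of fitted GEEs (1,000 runs, ρ = 0.7) gave 7.8% with complete pairs. With 4 second drives missing it gave 7.7% under independence and 8.1% under exchangeable. The Monte Carlo error is about 0.8 points. The t-based within-subject test, standing in for the mixed model, held about 5%.

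**2. Precision, random drop-out.** Let n = 12 per sequence, m the number with both drives and d₀ = n − m the number missing drive 2.

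- Independence GEE: Var = 2(n + m − 2ρm)/(n + m)²
- Random-intercept model at known ρ (equally, exchangeable weighting): Var = 1/[m/(1 − ρ) + d₀/2]
- Complete pairs only: Var = (1 − ρ)/m

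With no missing drives, m = n = 12 and all three equal (1 − ρ)/12, so the ratio is 1.000 at every ρ.

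With 4 of 24 missing (17%; m = 10, d₀ = 2):

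| ρ | Independence | Mixed / exchangeable | Ratio |
|---|---|---|---|
| 0.5 | 24/484 = 0.0496 | 1/21 = 0.0476 | 1.041 |
| 0.7 | 16/484 = 0.0331 | 1/34.33 = 0.0291 | 1.135 |
| 0.8 | 12/484 = 0.0248 | 1/51 = 0.0196 | 1.264 |

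At ρ = 0.7 the standard errors are 0.182 (independence), 0.171 (mixed) and 0.173 (complete pairs only). Independence weighting there does worse than discarding the unpaired drives. In 300 simulated trials of this case, the SD of the estimate was 0.175 for exchangeable GEE, 0.175 for the mixed model and 0.190 for independence GEE.

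**3. Drop-out depending on the first drive.** In simulation (12 + 12, 4,000 runs, about 15% missing) the variance ratio, independence to exchangeable, ran from about 1.11 to 1.48 over ρ = 0.5 to 0.8. Bias under independence was about 0.01 to 0.02 SD. Against an assumed effect of 0.5 SD, that is 0.01/0.5 = 2% to 0.02/0.5 = 4%. Exchangeable weighting left little or none.

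**The case against.** The strongest reply is that this is loose wording with little consequence. Choosing a working structure and adding a robust variance is ordinary GEE practice. Section V says that structures will be specified, and it nowhere says independence. Exchangeable GEE matches the mixed model's precision for Gaussian outcomes, and complete pairs show no loss at all. A population-averaged effect is also a legitimate target.

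Most of this stands, and it rules out several stronger readings.

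- A reader might infer that GEE, or the unnamed structure, by itself makes the analysis less precise. It does not. The loss needs both an independence structure and missing second drives, and the plan states neither.
- A reader might infer that Section V confuses the working covariance with the Huber-White variance. The sentence can fairly be read as using one together with the other. Its fault is that it leaves the structure unnamed.
- A reader might infer that odds ratios will be attenuated relative to within-person ones. Marginal and subject-specific logit coefficients do differ, but no binary endpoint is defined. The primary measures are glance behaviour, heart rate and skin conductance.

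The reply does not answer the test size. The 7.4% arises with complete pairs and is no better under an exchangeable structure. Section V does not say outright that a normal reference will be used; that is the usual reading of a Huber-White analysis with no correction stated.

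**Conclusion.** The concern holds in a limited form. Section V prescribes two different models, does not say which governs, and names no working correlation. Carried out literally as GEE with uncorrected robust z-tests on 24 subjects, it has a true level of about 7–8% at an assumed nominal 5%, even with complete data.

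A further loss is conditional. If independence were chosen and about 15% of second drives were missing, the variance would be about 1.04 to 1.26 times that of the mixed model under random drop-out. It would be up to about 1.5 times if drop-out depended on the first drive, with bias of a few percent of the effect. These figures rest on assumed ρ of 0.5 to 0.8 and an assumed drop-out rate. Exchangeable GEE largely removes this part, but not the inflated test size. Point estimates for Gaussian measures with complete pairs are unaffected. This should be changed before analysis; it does not invalidate the design.

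**What to change.** For heart rate, skin conductance and continuous gaze measures, replace the GEE sentence with: linear mixed model with fixed effects for treatment and period and a random subject intercept, fitted by REML, with small-sample degrees of freedom (for example Kenward-Roger). Say that subjects with one drive are kept in the model.

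Keep GEE only for outcomes actually defined as binary or count. Give them an exchangeable working correlation and a small-sample-corrected robust variance, and label their effects population-averaged. Rewrite the Huber-White sentence so that it names the working structure and the correction; do not delete it.

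The cost is a few sentences in Section V and a different procedure call, with no change to recruitment, visits or data. The downside is that the mixed model relies on its covariance model, which for two visits is a single correlation.

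### The plan tests a 24-subject AB-BA crossover by GEE with Huber-White variance and fixes no small-sample correction, reference distribution or period term; the ordinary form with treatment and period has 7.4% type I error for Gaussian outcomes.

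*Combined protocol and SAP*

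**What the plan says.** Section V (Biostatistical Analysis) is the whole of the analysis plan. It refers to random regression models and then states "We will estimate our RRMs using the generalized estimating equation (GEE) framework". For continuous outcomes, "for normally distributed data, linear regression models will be fit with the Gaussian distribution and identity link". On variance: "Working covariance structures will be specified with Huber-White robust estimators of variance to account for repeated measures of each subject". Binary and count outcomes get logit and log links.

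Section I describes a "randomized cross-over trial of treatment with buspirone for 2 days before and during the simulation in 24 HF-ASD subjects using an AB-BA design", and section III repeats the number: "We propose to enroll 24 adult drivers with HF-ASD". Under Driving Simulation Visits in section IV, half the subjects do the medicated drive first and half do it second, so each subject contributes one medicated and one unmedicated visit. The same part of the plan names eye glance behaviour, heart rate and skin conductance as the primary dependent measures.

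Neither section V nor any other section gives a small-sample correction, a normal or t reference, degrees of freedom, a list of model terms (treatment, period, sequence) or an alpha level.

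**The concern.** The Huber-White variance is justified when the number of independent clusters is large. Here there are 24. Its residuals come from a fitted model, so they are too small on average, and without correction the variance is underestimated. A normal reference then ignores the uncertainty in that variance. Both errors make the test liberal.

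The missing period term is a separate omission that works the other way. In a balanced AB-BA trial, leaving period out does not bias the treatment estimate, but any real shift from the first to the second visit enters the residual variance and makes the test conservative. Such a shift is plausible. The plan includes an adaptation drive so that subjects can "become accustomed to the mechanisms of the simulator and to reduce the novelty of driving the simulator", which shows that familiarity with the simulator was expected to matter. The plan does not say how large the shift might be.

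As written, the same data could give different p-values according to the software's default variance and reference distribution and whether period is in the model. Nothing prevents those choices from being made after the data are seen.

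**Working it through.** The plan states no error rate, so there is no figure of its own to reproduce.

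**Inputs from the documents.** n = 24 (sections I and III); equal split, so m = 12 per sequence; two visits per subject; GEE with Gaussian identity link and robust variance (section V).

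**Assumptions.** Two-sided 5% test, normal outcome, one value per visit, all 24 complete. Visit shifts are in SD of the within-subject difference.

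**Treatment plus period.** The treatment estimate is half the difference between the two sequence means of the within-subject (visit 1 minus visit 2) differences. The plain sandwich divides each sequence's sum of squares by 12 where the unbiased variance divides by 11. Its variance is therefore 11/12 (that is, 22/24) of the unbiased one, and the robust z equals t(22) × √(12/11).

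- Size = P(|t(22)| > 1.96 × √(11/12)) = P(|t(22)| > 1.877) = **7.39%**.
- Interval width relative to exact = 1.877 / 2.074 = 0.905, so 9.5% too narrow.
- An exact p of 0.050 (|t| = 2.074) becomes z = 2.074 × √(12/11) = 2.166, reported p = 0.030.

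**Treatment only, no visit effect.** The plain variance is 23/24 of the unbiased one.

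- Size = P(|t(23)| > 1.96 × √(23/24)) = P(|t(23)| > 1.919) = **6.75%**.
- Width ratio = 1.919 / 2.069 = 0.928, so 7.2% too narrow.
- An exact p of 0.050 is reported as 0.035.

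**Readings the plan permits (size, no visit effect).**

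| Variance and reference | Treatment + period | Treatment only |
|---|---|---|
| Plain, normal | 7.39% | 6.75% |
| n/(n-1), normal | 6.83% | 6.22% |
| Plain, t(23) | 6.03% | 5.46% |
| n/(n-1), t(23) | 5.54% | 5.00% |

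The last cell, 5.00%, is the ordinary paired t-test.

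**Unmodelled visit shift (simulation, 400,000 replicates per shift).**

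| Assumed shift (SD) | Treatment only, plain, normal | Treatment only, paired t |
|---|---|---|
| 0.25 | 5.9% | 4.3% |
| 0.4 | 4.9% | 3.5% |
| 0.5 | 4.2% | 2.9% |
| 1.0 | 1.0% | 0.6% |

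The treatment-only plain form crosses 5% at a shift of about 0.39 SD. With period in the model, the plain form stays at 7.3% to 7.4% at every shift.

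**Independent checks.** A separate simulation of 200,000 trials gave 7.38% for treatment plus period. Fitting an actual GEE routine to 3,000 simulated trials gave 7.1% (Monte Carlo SE about 0.5 points).

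**Dropout.** For treatment plus period with equal sequences, the plain form gives 7.6%, 7.9% and 8.8% with 22, 20 and 16 completers.

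**After correction.** The Kauermann-Carroll adjustment scales each residual by 1/√(1 - 1/12). This restores the factor 12/11 to the variance, so with a t(22) reference the test is the AB/BA t-test and its size is 5.00%. On one simulated data set the corrected standard error was 0.28531, identical to the AB/BA t-test, against 0.27316 for the plain form; (0.28531/0.27316)² = 1.091 = 12/11.

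**The case against.** The strongest reply is that 7.4% is the top of a range. It needs the plain sandwich, a normal reference and a period term, and the plan commits to none of these. With other permitted choices and no visit effect the size can be as low as 5.0%, and with a real but unmodelled visit shift the test is conservative. The excess is at most 2.4 points at 24 completers, the estimate is unbiased, and alpha itself is assumed. All of this is correct. It makes the 7.4% conditional, but it does not remove the defect, which is that the plan leaves the error rate open in both directions.

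The figures may also miss the main aim, which section II ties to eye tracking. Of glance data the plan says only "Eye glance behavior will be coded from the in-cab video recordings and reduced to numeric values prior to further analysis". If these become counts or binary outcomes, the Gaussian figures do not apply. This stands. The figures cover heart rate and skin conductance if these are roughly normal after the individual-variability transforms that section IV allows, and glance measures only if they are analysed as Gaussian.

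Finally, the remedy is exact only for equal sequences and complete pairs, and not every GEE package offers the Kauermann-Carroll variance. Both points stand. With 12 and 8 completers the corrected test has about 5.2% size, and with 12 and 6 about 5.8%, against about 8.3% and 9.6% for the plain form. It remains the better choice. Where the option is missing, the AB/BA t-test gives the same answer for balanced, complete continuous data.

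**Conclusion.** The concern holds. Section V commits the tests to a large-sample variance estimator on 24 clusters and fixes none of the choices that determine its small-sample behaviour. For Gaussian outcomes with 12 complete pairs per sequence, one value per visit and a nominal two-sided 5% test, the ordinary form is too liberal when period is modelled. When period is left out, it ranges from too liberal to strongly conservative, depending on a visit effect of unknown size. That the plan is silent on these choices is certain, and so is the algebra; which form would actually be run is not known. The practical effect is on borderline results for primary measures. The plan should be changed, but the treatment estimate itself is not called into question.

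**What to change.** Keep GEE clustered on subject. State that each model contains treatment and period. For continuous outcomes, pre-specify a small-sample-corrected sandwich (for example Kauermann-Carroll) with a t reference on n-2 df, 22 at n = 24, and state alpha and sidedness. For count and binary outcomes, name the small-sample correction in advance; the size calculations here do not cover them.

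The cost is one or two sentences, plus a check that the chosen software offers the correction. Intervals become 10.5% wider than the plain form with treatment plus period (1/0.905 = 1.105), and p-values rise slightly. Where the corrected test has 80% power (noncentrality 2.93, a true effect of 2.93/√24 = 0.60 SD of the within-subject difference), the plain form would reject 85% of the time. That 5-point gap comes from the inflated error rate, so giving it up loses no legitimate power. If a real visit effect exists, including period also recovers the power that a treatment-only model would lose.

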## II. SPECIFIC AIMS

Main Aim: To examine the effects of treatment with the anti-anxiety medicine buspirone on driving performance (eye tracking) in individuals with HF-ASD.

**Hypothesis:** We hypothesize that, compared to the untreated performance, treatment with buspirone will improve 1) physiologically measured hyperarousal (through heart rate and skin conductance) and 2) driving performance (eye tracking deviations) while performing a simulated driving task in a driving simulator.

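### Section V names no model terms for the two-visit AB-BA crossover in 24 subjects: a period term is left open, and the robust variance has no small-sample correction

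*Combined protocol and SAP*

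**What the plan says.** Section I describes a randomized cross-over trial "in 24 HF-ASD subjects using an AB-BA design". Under Driving Simulation Visits in Section IV, "Half of eligible and consenting subjects (A-B group) will be tested on the driving first on medication" and the other half are tested unmedicated first.

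Section V is the whole analysis plan. It names random regression models estimated by GEE, canonical links for binary, count and normal outcomes, and a variance method: "Working covariance structures will be specified with Huber-White robust estimators of variance to account for repeated measures of each subject". It lists no fixed effects at all: not treatment, period, sequence or carryover. It names no reference distribution and no small-sample correction.

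The only contrast stated anywhere is in the Section II hypothesis: "compared to the untreated performance, treatment with buspirone will improve" arousal and driving performance.

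Two other statements in Section IV might seem to deal with visit order, but neither does. For the sensor data, "statistical computations for physiological data will be completed based upon transforms designed to control for individual variability", which concerns differences between people. Subjects are introduced to the simulator "through a brief adaptation drive of approximately 10 minutes", a period intended among other things "to reduce the novelty of driving the simulator". That is a reduction, not a claim of removal.

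**The concern.** A two-period crossover compares each subject with himself or herself at another visit. Anything that changes between visits, such as familiarity with the simulator, therefore enters each treated-minus-untreated difference, with opposite signs in the two sequences. Randomizing the order balances this on average but does not take it out of the error. A period term does.

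The protocol's own timings make a shift possible. Before the main drive at visit 1 a subject has had about 10 minutes in the simulator. Of the main drive, Section IV says that "the duration of the primary drive should run for approximately 45 minutes". So before the main drive at visit 2 the total is about 10 + 45 = 55 minutes, or 65 if the adaptation drive is repeated. The outcomes are eye scanning, heart rate and skin conductance, which familiarity could plausibly move.

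At stake are power in a trial of 24, bias if one sequence completes less often than the other, and the freedom to choose the model after seeing the data. Sandwich variance also tends to be too small with so few clusters.

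**Working it through.** **Inputs.** From the documents: N = 24, half per sequence (taken as 12/12), two visits. The documents give no alpha, power, effect, SD, visit shift or dropout rate, so there is no figure of the plan's own to reproduce. Assumed: two-sided alpha 0.05; SD of the within-subject difference = 1; effect tau = 0.598 (80% power at 12/12 with 22 df); visit-2 improvement p from 0 to 1, in the same SD units.

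**Model.** Let D be treated minus untreated, signed so that positive is better. A-B subjects have mean tau - p and B-A subjects tau + p.

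- Period omitted: the estimate is the mean of all D. Its expectation is tau + p x (nBA - nAB)/N. With equal completion the expected sample variance of D is 1 + p² x N/(N-1).
- Period included: the estimate is (mean D in A-B + mean D in B-A)/2. Its expectation is tau for any p, with pooled within-sequence SD and N-2 df.

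**Equal completion, 12/12, Gaussian model.** The bias is p x 0/24 = 0. At p = 0.5 the variance is 1 + 0.25 x 24/23 = 1.261 (SD 1.12). At p = 1.0 it is 1 + 24/23 = 2.043 (SD 1.43). The estimate itself is no more variable; its standard error is overstated, so the test becomes conservative. Simulated t-test results:

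| Shift p | Power, omitted | Power, included | Null rejection, omitted | Null rejection, included |
|---|---|---|---|---|
| 0 | 80% | 80% | 5.0% | 5.0% |
| 0.25 | 78% | 80% | 4.3% | 5.0% |
| 0.5 | 73% | 80% | 2.9% | 5.0% |
| 1.0 | 50% | 80% | 0.6% | 5.0% |

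**Unequal completion, complete pairs, p = 0.5.**

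| A-B/B-A completers | Bias, omitted | Rejection at tau = 0.598, omitted | Included |
|---|---|---|---|
| 12/8 | 0.5 x (8-12)/20 = -0.10 | 47% | 70% |
| 8/12 | 0.5 x (12-8)/20 = +0.10 | about 77 to 78% | 70% |

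At 8/12 the higher rejection rate comes from an inflated estimate. Under the null, the drug-favouring tail is about 4% instead of 2.5%. In a milder case, 12/10, the bias is 0.5 x (10-12)/22 = -0.045 SD, with power of about 61% omitted and 76% included (effect 0.6). If GEE keeps the visit-1 records of four subjects who leave one sequence, the size of the bias is p x (0.10 + 0.10 x working correlation). At p = 0.5 that is 0.05 to 0.075 SD for working correlations of 0 to 0.5.

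**Logistic model, equal completion.** Assumed log-odds: intercept -1, treatment 1, period 2. Untreated, the average probability is (0.269 + 0.731)/2 = 0.500, logit 0. Treated, it is (0.500 + 0.881)/2 = 0.690, logit 0.80. Without period the treatment coefficient is therefore 0.80 instead of 1.00, although the sequences are balanced.

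**Small-sample variance, Gaussian model, no shift.** Uncorrected Huber-White with a normal reference rejects a true null 6.8% of the time (period omitted) or 7.4% (included) at 12/12, and 7.1% or 8.3% at 12/8. With period included, the Kauermann-Carroll correction and t on N-2 df give 5.0% at 12/12 and 5.2% at 12/8.

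**The case against.** The strongest reply is that nothing here is shown to be wrong. Section V omits every term, including treatment, so the missing period term is one part of an unstated model rather than a decision to leave it out. A competent analyst of an AB-BA trial may well include it. The harm needs a treatment-only fit and a visit shift of unknown size, and bias in the Gaussian model also needs unequal completion. At a shift of 0.25 SD with equal completion the loss is about 2 power points, and omission makes the t-test conservative rather than liberal. All of this stands, and it makes the point conditional.

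Three stronger readings are tempting but unsupported.

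- That the plan analyses treated versus untreated only. The Section II sentence is a hypothesis, not a model statement.
- That any visit shift lowers power. This holds with equal completion, but at 8 A-B/12 B-A rejection rises from 72% with no shift to about 77 to 78% at 0.5 SD.
- That one sequence will lose more subjects. Section VI lets participants stop at any time, but nothing suggests that stopping will differ by sequence.

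In the other direction, balance is not a complete defence. Equal completion keeps the treatment-only estimate unbiased under the identity link, but not under the logistic model that Section V also plans.

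It is also fair to say that the small-sample variance is a separate matter from the period term. The roughly 7% rate rests on an assumed normal reference, and it is slightly worse with the period term than without. It is raised here because both gaps lie in the same model statement and should be closed together.

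**Conclusion.** The concern holds as a gap in specification. The absence of model terms and of a small-sample correction is certain from the text; the consequences are conditional on a treatment-only fit and on the assumed values.

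For the Gaussian model at 12/12, that fit costs about 2 power points at a 0.25 SD shift, 7 at 0.5 and 30 at 1.0, with no bias. With unequal completion it adds bias in a direction set by which sequence is depleted. The 12/8 and 8/12 cases illustrate this and are not forecasts.

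The period term has limits. A carryover c into the untreated visit of A-B shifts the estimate by -c/2 with or without it. It also does not correct dropout related to outcome. The gap should be closed before analysis, but the crossover design itself is not in question.

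**What to change.** In Section V, state the primary model as outcome = treatment + period (visit 1 or 2), with subject as the cluster, and use the same terms in the Gaussian, logistic and Poisson models. Report the period estimate beside the treatment estimate. Name a small-sample-corrected sandwich, for example Kauermann-Carroll, with a t reference on N-2 df. State that the treatment estimate assumes no carryover and dropout unrelated to outcome.

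This is a short addition to the text and needs no new data. If there is no visit shift, the period term costs 0.2 power points at 12/12 (80.2% to 80.0%) and 2.0 points at 12/8 (71.9% to 69.9%) with a t-test; Kauermann-Carroll with t costs the same. Mancl-DeRouen with t is an alternative, but it is conservative (null rejection 4.1% at both) and costs more power: 77.4% at 12/12 and 65.8% at 12/8 with period included. The small-sample figures were worked out for the Gaussian model only.
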